7.0 Setting

MUSC dermatology clinics

8.0 Recruitment Methods

Recruitment will occur during standard of care visits to the Dermatology and Pediatric Dermatology Clinics, virtual visits, and chart review of eligible patients.

For standard of care visits, someone directly involved in the participants patient care will assess the patient's eligibility and inform eligible patients and/or their legal guardian about this study. If they are interested, the study team members will approach the patients or their legal guardian without coercion and with the emphasis on the voluntary aspect of being on this study. Subjects will also be told in a caring manner that no matter what their decision is, it will not affect how their doctor cares for them as a patient or their care in general.

Potential subjects who contact the study team members directly will also be considered for participation in the study. In this event, these potential subjects must have heard about the study through indirect information sources (clinicaltrials.gov or other means by which the study team members did not directly advertise the study for purposes of recruitment). If they

Page 7 of 13

are interested, the study team members will respond to them via email, and subsequently approach the patients virtually without coercion and with the emphasis on the voluntary aspect of being on this study. Subjects will also be told in a caring manner that no matter what their decision is, it will not affect how their doctor cares for them as a patient or their care in general.

9.0 Consent Process

Potential subjects and/or their legal guardians will be approached by researchers at MUSC Dermatology and Pediatric Dermatology clinics. Members of the team will approach their own patients to ask for participation. Pertinent project information, risks and time commitment will be relayed to subjects. If subjects show interest in participating, they will be given an assent form to either sign or bring home for consideration.

Minimally, an adult parent with legal custody of a child or an adult awarded legal custody of a child must give informed consent for a child to be enrolled in research. A child 12 years of age or older must give documented "assent" to be enrolled in research. The assent will be documented on the informed consent document. An "emancipated minor" must provide documentation of his/her financial independence such as a rental lease, marriage certificate or court document in his/her name proving emancipation before consenting as an adult to participate in research. If child reaches 18, while enrolled on the study they will be reconsented without parents. All patients 18 years and older will be consented as adults.

The consent process will occur in a private room; the research team will explain to the participant and/or their legal guardian a language they can understand what it means to take part and what they can expect. Research team members will be obtaining assent when applicable. The research team will use language and terminology that will be understood by participant. A device demonstration will be showed to the child and their parents. The child and parents will be encouraged to ask questions at the end and sign their understanding. No waiting period will be necessary between informing the subjects and obtaining the consent however, subjects will be allowed to take home the unsigned consent form for review prior to signing it if needed and reschedule another visit for treatment as soon as possible.

10.0 Study Design / Methods

- A chart review of patient the patient's medical record will be completed and the following information will be collected for research purposes: DOB, demographics, contact information and diagnosis.
- Skin irritants, emollients, topical medications and other topical products cannot be applied to the study area 4 weeks prior to the start of the study and throughout the duration of the study. Details of what can and cannot be used can be discussed any time.
- During a clinical care visit, if a patient is eligible and agrees to participate, lesions will be selected by the dermatologist prior to procedure. The lesions will be marked randomly for a certain treatment regimen and photographs will be taken before each treatment and after completion of the study. Identifiers will be covered to protect identity. All images will be saved on a MUSC network secure box drive using a subject study number.
- The number of lesions treated will not exceed SOC recommendations. They will be determined by provider assessment and anatomical location.
- Participants with one lesion will receive either NTAP or standard of care (SOC). SOC is

Page 8 of 13

cryotherapy for warts and cantharidin for molluscum. Participants with greater than 2 lesions will receive equal treatment of NTAP and SOC. The number of lesions treated will be based off the providers assessment and anatomical location. Treatment of a single lesion or an odd number of multiple lesions will be based off a randomized list.

- All SOC lesions will be treated first to reduce the number of patients not wanting return to the more painful modality.
- All people in the room will be provided eye shields that must be worn during treatment. The patient will be placed in a comfortable position before the lesion is cleaned with alcohol.
- Each lesion will be treated for 1-2 minutes. Total treatment duration will be no longer than 20 minutes.
- The interval between treatment groups will about 1 minute.
- There will be a follow-up phone call a week after treatment to check on resolution and report any adverse events. If an adverse event is reported the study team members will access if the patient needs to be seen by a provider that day.
- Patient will return to the office for a 4-week standard of care follow-up. Study cessation or additional treatment will be determined by the provider assessment of lesion clearance. If lesion persist another treatment will occur. No greater than 3 treatments will be performed.
- This study will be single blinded, meaning the study team member accessing the results will
 not know which lesions were treated with what therapy. Assessment of clearance will be based
 off of clinical examination and images. The team will record any additional clinical feature
 that may arise during the analyses.

11. Data Management

- Continuous data will be summarized using descriptive statistics (number of values, means, standard deviation, median, minimum and maximum). Categorical data will be summarized using frequency tables (frequencies and percent).
- Chi-square analysis comparing the proportions of successes (equal chance outcomes).
- Coded dermoscopic and clinical photographs may be obtained for further analyses after each visit. Files with patient images will be stored in a secure departmental drive that will only be accessible to study team members by their unique MUSC ID and password.
- All subject medical record information and data collection will be coded and stored on an MUSC Box drive only accessible to study team members and will be protected by two-factor authentication. The linking document between ID and PHI will be maintained separately from the study data in a separate encrypted folder.

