3.0 Intervention to be studied (if applicable)

We will utilize a floating electrode-dielectric barrier device (FE-DBD) Cold atmospheric plasma (CAP) device on molluscum and warts in children and adolescents 4-21 years (Figure 1). Children and adolescents are targeted because they are the population most affected by painful standard of care therapy. The study will continue until at least 68 warts and 68 molluscum are treated. Each patient will not have more lesions treated than SOC recommendations. Half the lesions will be treated with plasma and the other half with standard of care being cryotherapy for warts and cantharidin for molluscum. A single patient must have minimum of 1 clinically diagnosed lesion treated and maximum of 20 treated. Lesions with a clinical impression of warts or molluscum will be selected. Selection of treatment type (control vs NTAP) will be randomly selected. Lesions

Page 3 of 13

The treatment device in this study generates cold atmospheric plasma. Cold atmospheric plasma has certain properties of plasma, such as ionized gas molecules. To create plasma, a pulse generator supplying 20-kV pulse of 20-ns pulse width at 200 Hz (FPG10-01NM10, FID GmbH, Burbach, Germany) to a 5-mm diameter quartz-covered copper electrode of 10-cm length and 1-mm quartz thickness (5). These nanosecond pulse parameters were chosen to provide sufficient treatment dose at the high level of plasma uniformity required to avoid any tissue damage. We treated the lesions for approximately 1 to 2 minutes each, moving the electrode gently over the treatment area.

After the study treatments are completed, we will analyze the data to see if the treatment was safe and effective.

Non-significant risk device statement (6-19) (Figure 1)

- We are proposing a clinical trial floating electrode-dielectric barrier device (FE-DBD) a Cold Atmospheric Plasma (CAP) device.
- While novel to the medical field and especially to dermatology, there are already a number of publications regarding its use on human skin in adults (20-26) and children (29).
- CAP devices utilize noble gases (such as helium) to deliver plasma state matter to the skin. As
 its name implies, the generated plasma stream is of near skin temperature and it exists on
 normal atmospheric pressure. During the generation of the plasma there is no electric contact
 with the patient. The treatment does not increase skin surface temperature and the used helium

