6.0 Number of Subjects

Total of 150 would be required (half control, half NTP) to achieve 80% power with an alpha of

.05.

Calculation:

- Assumption for Probabilities for the Null hypotheses is P1=P2=P3=1, hence P1 = .333333, P2 = .333333, P3 = .333333 and P1+P2+P3 = 1.0 or that each proportion has an equal chance.
- Assumption for Probabilities for Alternative Hypothesis is taken from Provided NTP paper where P1=9/17 (Full Resolution = .53), P2=3/17=.18 (Some Improvement), and P3=5/17=.29 (no improvement).

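### The randomised list is specified only for single and odd lesion sets; for even sets the random marking has no stated sequence, responsible person or concealment

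*Combined protocol and SAP*

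**What the plan says.** Section 3.0 (Intervention) states the aim for all lesions: "Half the lesions will be treated with plasma and the other half with standard of care", and "Selection of treatment type (control vs NTAP) will be randomly selected". It sets separate minimum targets of 68 warts and 68 molluscum, names a different control for each disease (cryotherapy and cantharidin), and allows 1 to 20 treated lesions per patient.

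Section 10.0 (Study Design / Methods) gives the mechanics:

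- At the visit, "lesions will be selected by the dermatologist prior to procedure".
- Then, "The lesions will be marked randomly for a certain treatment regimen". The sentence is passive and names no one.
- A participant with one lesion receives one treatment or the other.
- "Participants with greater than 2 lesions will receive equal treatment of NTAP and SOC".
- "Treatment of a single lesion or an odd number of multiple lesions will be based off a randomized list".
- On blinding: "This study will be single blinded, meaning the study team member accessing the results will" be unaware of the therapy given to each lesion. No blinding of the people who mark or treat is described.

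Section 11 (Data Management) plans a chi-square comparison of proportions. It mentions no adjustment for lesion features.

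**The concern.** Where a child has several lesions, the treatments are compared between lesions of the same child. An equal split then balances what belongs to the child, such as age or immune status. It does not balance what belongs to the lesion: size, thickness, site, tenderness. Those features are visible to anyone marking lesions at the visit.

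Random marking protects against steering only if the assignment comes from a sequence that the marker can neither foresee nor alter. For even sets the plan describes no such sequence. The team also expects standard care to hurt more, since Section 10.0 has those lesions treated first for that reason. In children this gives an understandable motive to send tender sites to plasma, which could affect the pain comparison as well as clearance. Bias of this kind does not shrink as the sample grows, and the planned chi-square test does not correct for it.

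**Working it through.** **Step 1. What is specified for each lesion count.**

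| Lesions in the participant | Split | How each lesion gets its treatment |
|---|---|---|
| 1 | NTAP or SOC | Randomised list |
| Exactly 2 | Only the general half-and-half statement in Section 3.0; the equal-split rule in Section 10.0 starts above two | Random marking, method not stated |
| Even, 4 or more | Equal | Random marking, method not stated |
| Odd, 3 or more | As equal as possible | Randomised list, but unclear whether it assigns every lesion or only the extra one |

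If the list settles only the extra lesion, the method is unspecified for most lesions in odd sets too. The documents do not describe how the list is built, so stratification by disease is not stated either way.

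**Step 2. Possible size.** The plan has no figure on this point. Its total is used only for scale: "Total of 150 would be required (half control, half NTP) to achieve 80% power with an alpha of" .05 (Section 6.0). I read this as 75 lesions per arm. Whether 150 is itself correctly derived is a separate question and does not affect the bias.

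Assumed inputs, none of them in the documents:

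- g, the clearance gap between the easier and the harder lesion of a pair: 20 points, range 10 to 30.
- p, the chance that the easier lesion goes to plasma: 0.6 to 0.7 (0.5 is fair allocation).
- No true treatment effect, clearance near 50%, every lesion in a steered pair, lesions treated as independent.

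Bias = (2p − 1) × g.

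- p = 0.6, g = 0.20: (1.2 − 1) × 0.20 = 0.04
- p = 0.7, g = 0.20: (1.4 − 1) × 0.20 = 0.08
- Over g = 0.10 to 0.30: from 0.2 × 0.10 = 0.02 to 0.4 × 0.30 = 0.12

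Standard error of the difference = √(2 × 0.25 / 75) = 0.0816.

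Two-sided rejection rate at .05 = P(Z > 1.96 − bias/SE) + P(Z < −1.96 − bias/SE).

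| Bias | Bias/SE | Upper tail | Lower tail | Total |
|---|---|---|---|---|
| 0.02 | 0.245 | 4.3% | 1.4% | 5.7% |
| 0.04 | 0.490 | 7.1% | 0.7% | 7.8% |
| 0.08 | 0.980 | 16.4% | 0.2% | 16.5% |
| 0.12 | 1.470 | 31.2% | 0.0% | 31.2% |

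**Step 3. Dilution.** If only a fraction f of lesions lies in sets open to steering, the bias is f × (2p − 1) × g. With f = 0.5 and g = 0.20 it is 2 to 4 points, and the rejection rate is 5.7% to 7.8%. The documents give no distribution of lesion counts, so f is unknown.

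**The case against.** A reader might infer that in even sets the treating dermatologist decides which lesions get plasma. The documents do not support that. They say that the dermatologist selects the lesions, and the marking sentence names no one. Two statements, one in Section 3.0 and one in Section 10.0, make assignment random for all lesions without exception. Non-random choice is not the plan. It is also fair to read the list sentence as covering the cases where an equal split is impossible, with even sets randomised by a method that was simply not written down.

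Two further inferences go too far. The list cannot be said to ignore disease, because its structure is not described. Nor can it be said that most of the randomisation occurs in even sets, because lesion counts are not given.

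The plan also has partial safeguards. Photographs are taken before each treatment, face, genital and self-resolving lesions are excluded, and outcomes are read blind. The illustration is a worst case in that it puts every lesion in a steered pair, and its inputs are assumed.

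All of this stands, and it limits the point to an unspecified method. It does not remove the point. Photographs could reveal an imbalance but not undo it, the exclusions narrow differences between lesions without abolishing them, and blind assessment comes after the allocation.

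**Conclusion.** The concern holds as a gap in the allocation method. For even sets the plan states random assignment with no sequence, responsible person or concealment, after the lesions have been chosen and by staff not described as blinded. Steering by size, site or tenderness cannot be excluded, though nothing shows that it is intended. The role of the list in odd sets, the rule for exactly two lesions and stratification by disease also need to be stated.

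The size is unknown. The figures of 4 to 8 points, and 8% to 17% false positives against 5%, illustrate one assumed setting. They fall in proportion to the share of lesions affected, and correlation between lesions of one child would change the error rates but not the bias. The change is worth making because it is cheap and because allocation bias cannot be repaired at analysis.

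**What to change.** In Section 10.0, use one pre-generated, concealed allocation for every participant, whatever the number of lesions:

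1. The dermatologist selects the lesions, and they are numbered in a fixed order (for example, anatomical) and recorded.
2. Only then is the next sealed or electronic entry opened. It assigns each numbered lesion to NTAP or SOC, half to each.
3. Warts and molluscum have separate lists, in line with their separate targets and controls.
4. For single-lesion participants and the extra lesion in odd sets, the lists are blocked with varying block sizes, so that unblinded staff at a single centre cannot predict the next entry.
5. The equal-split rule is reworded from more than two lesions to two or more.
6. The protocol names who generates the list, who holds it and who opens the entries.

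Fixed-order numbering is one workable method; another that fixes lesion identity before the assignment is revealed would also do. The cost is a longer list and sealed or electronic entries. Visits, sample size and treatments are unchanged.

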1.0 Study Endpoints (if applicable)

- Clinical assessment response after 4, 8 or 12 weeks. This will be assessed by a blinded study team member comparing clinical photographs and dermascopic images.
 - Clinical photographs measured by no response, partial resolution, complete resolution.
 - Dermoscopy images: no response, partial resolution, complete resolution using the guidelines below that indicate the presence of wart or mollusum.
 - Molluscum: Visualization of a central umbilication with polylobular, white to yellow, amorphous structures is typical. A peripheral crown of radiating or punctiform vessels is also present.
 - Wart: grouped papillae, with dotted or loop vessels, and/or hemorrhagic points and lines often surrounded by a whitish halo
- Visual analogue scale for experimental treatment and control treatment
 - The visual analogue scale (VAS) is a validated subjective measurement of pain experienced by the patient. It consists of visual-numeric scale, numbered from 0-10. (0) indicate absence of pain or "no pain at all", while (10) indicates severe pain or "worst imaginable pain". This is supplemented by six faces with different expressions, ranging from happy to extremely upset. Each facial expression is assigned a numerical scale from 0 to 10.
- Evaluation of tolerability included assessment of dry ness, peeling, scaling, erythema, edema, stinging, burning sensation, itching, scaring and dyspigmentation. They will be assessed by means of a standardized grading scale (0 = absent; 1 = mild; 2 = moderate; 3 = severe)

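### In sessions that use both treatments, standard of care always comes about 1 minute before NTAP, so the pain comparison is treatment plus order, and the planned summaries do not specify how to handle this

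*Combined protocol and SAP*

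**What the plan says.** Pain is an endpoint for both treatments. The Study Endpoints section lists "Visual analogue scale for experimental treatment and control treatment", scored 0 to 10. Risks to Subjects (15.0) has pain assessed at every treatment session. The hypothesis in Objectives / Specific Aims calls NTAP a painless alternative to cryotherapy.

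Study Design / Methods (10.0) sets the sequence: "All SOC lesions will be treated first to reduce the number of patients not wanting return to the more painful modality". It adds: "The interval between treatment groups will about 1 minute". Lesions are marked at random for a treatment, but the order of treatments is not randomized.

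The same section says who receives both treatments: "Participants with greater than 2 lesions will receive equal treatment of NTAP and SOC". A participant with one lesion receives one modality only, and "Treatment of a single lesion or an odd number of multiple lesions will be based off a randomized list". At the 4-week visit, "If lesion persist another treatment will occur", up to three treatments in all.

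For analysis, Data Management (section 11) states: "Continuous data will be summarized using descriptive statistics", namely number of values, mean, standard deviation, median, minimum and maximum. The only test named is a chi-square on success proportions. Pairing, order and single-lesion participants are not mentioned.

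**The concern.** A participant who receives both treatments in a session always scores NTAP after SOC. If NTAP scores lower, the device may hurt less, or it may seem mild after the treatment the protocol itself calls more painful. If NTAP scores higher, residual pain or distress from SOC a minute earlier may be the cause. Nothing in the documents tells these apart or fixes the direction.

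At stake is the pain part of the hypothesis. A mean VAS per modality, reported as planned, invites attribution of the difference to the device, which two-modality sessions cannot support. Meanwhile the design already creates a group without this problem in its first session, the single-lesion participants allocated from a randomized list, and no planned summary sets them apart.

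**Working it through.** The plan gives no figure for the pain comparison, so there is none to reproduce. The 150 in Number of Subjects (6.0) rests on resolution proportions, not on VAS.

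**1. Can treatment and order be separated?** Code each score as (intercept, NTAP, second position).

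- Two-modality session: SOC = (1, 0, 0) and NTAP = (1, 1, 1). The last two columns are identical, so the rank is 2 of 3 and only treatment + order can be estimated.
- Add single-lesion participants in their first session: SOC = (1, 0, 0) and NTAP = (1, 1, 0). The rank becomes 3, so the effects can be separated, provided the treatment effect is the same in single- and multi-lesion participants.

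Later sessions are a different case. One that re-treats only NTAP lesions has no SOC just before it, but which participants have such a session depends on which lesions persisted.

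**2. How far does an order effect move the contrast?** Let x be the order effect in VAS points and s the share of scores from single-lesion participants, taken as equal in both modalities. The shift in the NTAP-minus-SOC difference is (1 − s)x.

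| s (assumed) | Shift |
|---|---|
| 0 (two-modality sessions only) | 1.00x |
| 25% | 0.75x |
| 50% | 0.50x |
| 75% | 0.25x |

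The shift does not depend on the number of participants.

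**3. How does that compare with the precision available?** The documents give no x, no VAS standard deviation and no number of pairs. Assume a paired-difference SD of 2 to 3 points. The 95% half-width is t(0.975, n − 1) × SD / √n, for n pairs within one disease. Intervention to be studied (3.0) gives at least 68 lesions per disease. Dividing by k lesions per participant, rounded down, assumes that every participant has the same k.

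| Basis | Pairs n | Half-width, SD 2 to 3 |
|---|---|---|
| 68 / 8 | 8 | 1.67 to 2.51 |
| 68 / 4 | 17 | 1.03 to 1.54 |
| 68 / 3 | 22 | 0.89 to 1.33 |
| 68 / 2 | 34 | 0.70 to 1.05 |
| 150 read as subjects, split evenly by disease, all two-modality | 75 | 0.46 to 0.69 |

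The k = 2 row applies only if the half-and-half rule in section 3.0 covers participants with exactly two lesions. Section 10.0 assigns both modalities only above two.

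For illustration, take x = 1. It lies inside the half-width at 8 and 17 pairs. At 22 and 34 pairs it exceeds the half-width if the SD is 2 but not if it is 3. At 75 pairs it exceeds it throughout. More pairs narrow the interval around treatment + order and do not move it towards treatment alone.

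**4. How precise is the single-lesion check?** With m participants per modality in one disease, the half-width is t(0.975, 2m − 2) × SD × √(2/m). At an assumed m = 10 and SD 2 to 3, this is 1.88 to 2.82 points on the 0 to 10 scale.

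**The case against.** The order is openly stated and has a reason, retention. That stands, and the point does not ask to change it. The reason does not address what the order does to the pain comparison.

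No VAS test or interval is planned, and painless could be read as a statement about the NTAP score alone. This is partly right: the contrast is inferred from an endpoint listed for both treatments and a hypothesis framed against cryotherapy, and is not a specified analysis. Still, two descriptive means side by side carry the same shift as a test would. It is also true that, with one score per modality per participant, pairing leaves the mean difference unchanged. It matters once an interval is added.

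Every size here is assumed, and a 1-point effect may be lost in the noise at small numbers. That stands and limits the severity.

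Some stronger readings are tempting but unsupported:

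- A reader might infer that the plan prescribes pooling single- and multi-lesion participants and discarding the pairing. Section 11 is silent on both. It does not specify, which is less than prescribing the wrong thing.
- A reader might infer that the whole VAS comparison is shifted by the full x. That holds only within two-modality sessions, and pooling dilutes it.
- A reader might infer that the order favours NTAP. The documents give neither a size nor a direction.

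**Conclusion.** The point holds for sessions that use both modalities. There the fixed order makes the NTAP-versus-SOC pain contrast treatment plus order, and nothing elsewhere in the documents corrects or labels this. The aliasing follows from the text alone. Its size does not: the shift is x within those sessions and (1 − s)x in a pooled summary, with x, s, the SD and the number of pairs all unstated. Severity is minor to moderate, because the pain claim is part of the hypothesis but the size of any distortion is unknown. A reader might extend the point to clearance or to the sample size. Clearance is judged later by a blinded assessor and the sample size rests on resolution proportions, so neither is affected.

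**What to change.** Add to section 11:

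(a) For participants who receive both modalities, summarise first-session VAS as one NTAP-minus-SOC difference per participant, with a 95% confidence interval. Do this separately for warts and molluscum, because SOC is cryotherapy in one and cantharidin in the other. State that the difference includes any order effect and is not attributable to the device alone.

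(b) Report first-session VAS in single-lesion participants by randomized modality and by disease, with the number in each group, as an order-free check. Do not pool it with (a).

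The treatment order is left alone. The cost is a few sentences of analysis text on data already planned, with no extra visit or participant.

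The limits should be stated. (a) labels the order effect but does not remove it. (b) may be small and imprecise, as step 4 of the working shows. Single-lesion participants may differ in disease extent, and only the results assessor is blinded, so their own pain scores remain open to expectation. (b) is a check and does not replace (a).

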1.0 Objectives / Specific Aims

- Objective: Study the safety and efficacy of uniform nonequilibrium, nonthermal atmospheric pressure plasma (NTAP)/cold atmospheric plasma device (CAP) in the treatment of molluscum contagiosum and vercurra (warts) in children 4-21 years.
- Aim:
 - Measure the changes in size, pain and appearance of verrucae and molluscum after 4, 8 and 12 weeks.
 - Evaluate the safety profile and patient tolerability of the treatment by analyzing potential side effects and pain levels, or lack thereof, with each treatment.
- Hypothesis: NTAP will be an equally efficient and painless alternative to cryotherapy for the treatment of molluscum and warts.

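### Participants judged cleared stop before weeks 8 and 12, so response at those weeks is not observed for them, and no rule says how they are counted

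*Combined protocol and SAP*

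**What the plan says.** **Time points.** The aims (1.0 Objectives / Specific Aims) are to "Measure the changes in size, pain and appearance of verrucae and molluscum after 4, 8 and 12 weeks". The endpoint section (1.0 Study Endpoints) has "Clinical assessment response after 4, 8 or 12 weeks", graded by a blinded reader: "Clinical photographs measured by no response, partial resolution, complete resolution". One section joins the weeks with *and*, the other with *or*. Neither names a primary time point.

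**Follow-up (10.0 Study Design / Methods).** "Patient will return to the office for a 4-week standard of care follow-up". At that visit, "Study cessation or additional treatment will be determined by the provider assessment of lesion clearance". A lesion still present is treated again, with three treatments as the limit. Week 4 is the only office follow-up described, and later visits arise only through retreatment. Photographs are due ahead of each treatment and once the study is finished.

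**Allocation (10.0).** A participant with one lesion gets one of the two treatments. Participants with several lesions get both in equal numbers, and a randomised list settles odd counts.

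**Analysis (11. Data Management).** One line gives a chi-square test of success proportions. It names no visit, no denominator and no rule for a lesion that has already cleared.

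**The concern.** Two stated rules conflict. The aims and endpoints call for response at weeks 8 and 12. The follow-up rule stops participants whose lesions are judged cleared, and nothing requires an image of them afterwards. Whether week-8 and week-12 data exist therefore depends on an outcome of treatment.

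If the later proportions are computed on whoever is still followed, randomisation no longer protects the comparison. The more effective arm loses its easily cleared lesions sooner, so what remains in it is harder to clear. Two of the three stated time points are affected. Recurrence after a participant stops is not seen at all.

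**Working it through.** The plan gives no clearance rate by visit. The 9/17 full-resolution figure in 6.0 has no assessment week, so there is no plan figure to reproduce here. All rates below are assumptions chosen to show the mechanism.

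**Inputs.** Three treatments, assessed at weeks 4, 8 and 12 (10.0 and the endpoint section). Assumed: half the lesions easy and half hard; clearance per treatment e = 0.9, h = 0.2 in arm A and e = 0.5, h = 0.2 in arm B; no recurrence.

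**True cumulative clearance.** The share uncleared after k treatments is R_k = 0.5(1−e)^k + 0.5(1−h)^k, and cumulative clearance is C_k = 1 − R_k.

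- A: R = 0.45, 0.325, 0.2565
- B: R = 0.65, 0.445, 0.3185

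**Lesion-level exit.** The proportion cleared among lesions still followed is (R_{k−1} − R_k) / R_{k−1}.

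| Week | True cumulative, A v B | Lesions still followed, A v B |
|---|---|---|
| 4 | 0.55 v 0.35 | 0.55 v 0.35 |
| 8 | 0.675 v 0.555 | 0.125/0.45 = 0.278 v 0.205/0.65 = 0.315 |
| 12 | 0.7435 v 0.6815 | 0.0685/0.325 = 0.211 v 0.1265/0.445 = 0.284 |

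The direction reverses at weeks 8 and 12. For single-lesion participants, lesion exit and participant exit are the same, so this calculation applies to them under either reading.

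**Participant-level exit.** A participant leaves only when every lesion has cleared, and all lesions of attenders are assessed. Let D be the probability that all had cleared by the previous visit. With equal lesions per arm, the observed proportion is (C_k − D)/(1 − D). The same amount leaves both numerators, so the direction is kept and the difference is multiplied by 1/(1 − D).

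- *One lesion per arm, lesion classes independent.* Week 8: D = 0.55 × 0.35 = 0.1925, giving 0.4825/0.8075 = 0.60 v 0.3625/0.8075 = 0.45. Week 12: D = 0.675 × 0.555 = 0.3746, giving 0.3689/0.6254 = 0.59 v 0.3069/0.6254 = 0.49. The week-12 difference is 10 points; the true one is 6.
- *One per arm, both in the same class.* Week 12: D = 0.5(0.99 × 0.75) + 0.5(0.36 × 0.36) = 0.4361, giving 0.545 v 0.435.
- *Four per arm, independent.* Week 12: D = 0.3746^4 = 0.0197, so 98% still attend. The result is 0.7238/0.9803 = 0.74 v 0.6618/0.9803 = 0.68, almost unbiased.
- *Four per arm, all eight in the same class.* Week 12: D = 0.5(0.7425^4) + 0.5(0.1296^4) = 0.1521, giving 0.70 v 0.62. Some bias returns when a participant's lesions behave alike.

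**How common is reversal under lesion-level exit?**

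- Raising arm A's hard-lesion rate to 0.3 removes it. R becomes 0.40 then 0.25, giving 0.15/0.40 = 0.375 v 0.315 at week 8 and 0.078/0.25 = 0.312 v 0.284 at week 12.
- It can also occur when A is better in both classes. With 0.9/0.1 v 0.5/0.05, the proportions among lesions still followed are 0.18 v 0.21 at week 8 and 0.11 v 0.15 at week 12, against a true 0.64 v 0.51 by week 12.
- A grid of 196 scenarios was run: easy share 0.2 to 0.8, easy rate in the worse arm 0.2 to 0.7, hard rate 0.05 or 0.1, both rates 1.25, 1.5 or 2 times higher in the better arm, and easy rates above 0.95 excluded. Reversal occurred in 29 (15%) at week 8 and 52 (27%) at week 12.

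**The case against.** A reader might infer that each lesion leaves the study when it clears, that all week-8 and week-12 data come from earlier failures, and that the comparison will therefore reverse. The documents do not support that reading.

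- The sentence before the cessation rule is about the patient, and stopping the study is most naturally a participant event. Section 10.0 never says that a cleared lesion is dropped while the child stays. A participant with one persisting lesion returns, and the completion photograph could include the cleared ones.
- Up to 20 lesions may be treated per participant (3.0). With several lesions per arm and participant-level exit, the direction holds and the bias can be negligible.
- The analysis line does not call for tests at each visit among remaining lesions. The *or* in the endpoint section can be read as each lesion's final status at whichever week it finished. Cleared lesions would then count as complete resolution, and no reversal arises.

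These points stand, and they limit the claim. They do not remove it. The final-status reading is not written down, and the *and* in the aims points the other way. It also leaves follow-up of unequal length and recurrence unseen. Single-lesion participants are eligible, and for them the unit of cessation makes no difference. Their share is not given. Single and odd lesion counts also break the equal split on which the favourable result rests.

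**Conclusion.** The point holds as a conflict between the stated time points and the stopping rule, with no denominator to resolve it. Participants judged cleared have no required week-8 or week-12 assessment, and a proportion among those still followed is conditioned on earlier failure. This follows directly from the text for single-lesion participants. For the rest it depends on the unit of cessation.

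Under the main assumed rates, the true week-12 comparison of 74% v 68% could appear as 21% v 28% (lesion-level exit) or 59% v 49% (participant-level exit, one lesion per arm: same direction, both arms understated, difference exaggerated). With four independent lesions per arm it would be almost unchanged. Reversal is possible but not the usual result, and the documents do not show that it will happen here. What they do show is that permissible readings can give materially different answers from the same data. The rule should be fixed before analysis.

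**What to change.** In the endpoint and analysis sections:

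1. Define the efficacy endpoint as clearance by week 12.
2. Keep every randomised lesion in the denominator of its assigned arm.
3. Carry forward as cleared any lesion that the blinded reader grades as completely resolved on the exit image. The completion photograph in 10.0 can serve for this.
4. Report weeks 4 and 8 as cumulative proportions on the same denominator.
5. State whether cessation applies to the lesion or to the participant.
6. Reconcile *or* in the endpoint section with *and* in the aims.

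This removes the bias described here under either exit reading. It costs about one paragraph, needs no extra visits and leaves the treatment rules as they are. The downside is that recurrence after exit is not observed. The result must be described as clearance by week 12, with no claim of durable response at week 12.
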